### Schema:

There are two groups currently active in this protocol. Group 1 includes a mid-treatment FMISO PET scan and FDG PET scan. Group 2 includes a sequential injection of F-FMISO and F-FDG. Both groups will have completed a routine pre-treatment FB and breath-hold F-FDG PET/CT and pre-treatment F-FMISO PET Scan.

- Group 1: Perform a routine pre-treatment free-breathing (FB) and breath-hold (for only one PET Field of View, i.e. an additional ~10 min of PET/CT imaging) F-FDG PET/CT. If the patient is planned to receive radiotherapy, the FB PET/CT scan will be used for RT planning.
- Group 2: Perform a routine pre-treatment free-breathing (FB) F-FDG PET/CT. If the patient is planned to receive radiotherapy, the FB PET/CT scan will be used to RT planning.
- Both groups will perform a pre-treatment dynamic F-FMISO PET scan (F-FMISO1). This scan will occur at least one day after the baseline F-FDG PET/CT scan, but prior to initiation of therapy. A baseline F-FDG PET/CT scan may be acceptable provided it is not earlier than one month prior to the F-FMISO study and will assist to define the field of view of the dynamic F-FMISO PET scan. If a CT is available to allow definition of the tumor region, then the F-FMISO may be performed before the FDG PET scan. Dynamic F-FMISO PET images will be corrected for breathing-induced artifacts allowing kinetic analysis to be performed for both the motion-corrected and the free-breathing dynamic PET image sets. The degree of hypoxia within the tumor volume will be estimated by the magnitude of the F-FMISO irreversible trapping rate constant.
- **Group 1 : F-FMISO2/FDG mid-treatment PET/CT:** Perform a mid-treatment dynamic F-FMISO (FMISO2) PET/CT (following the same protocol as for the baseline FMISO) scan in a group of twenty five patients, undergoing RT or concurrent chemo-RT. This scan will occur two weeks +/- 4 days after the start of radiotherapy or the radiation portion of combined chemo-radiation (Diagram 1).

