## **9.2 F-FMISO PET/CT Scan Protocol:**

The first F-FMISO PET/CT scan will be performed within 14 days (+/- 5 days) after the baseline F-FDG scan, and before starting therapy. Dynamic FMISO PET scans will be performed on one of the GE Discovery PET/CT scanners residing in the nuclear medicine department at MSKCC. The patient will be set up in treatment position with intra-venous lines for radiotracer injection and for venous blood sampling. One 370 MBq (10 mCi) +/- 10% dose of F-FMISO will be injected as a bolus, and the dynamic scan initiated coincident with the injection.

Dynamic F-FMISO PET data will be acquired in List Mode and reconstructed in time frames that display the kinetics of tumor uptake. The total duration of the study is approximately 3 hours. The patient is injected in the PET scanning position on the couch and PET data acquired from 0-40 min. The patient is then allowed to return to the waiting room and rest. There are two further scan segments at approximately 90 min and 180 min post injection each of 10-minute duration. The total PET scan time within the 3 hour imaging session is therefore only 60 minutes. No further radioactivity will be injected for the 2nd and 3rd PET scan segments. In all three sessions of the dynamic PET study, the patient's breathing signal will be recorded simultaneously using the in-house developed tracking described previously. The respiratory signal will be used to retrospectively identify those PET events that occurred at end-expiration. Those events will be selected retrospectively to generate a dynamic PET data set corresponding to end-expiration (BH-dyn PET), motion-free PET images.

In each of the three dynamic sessions, a 4D-CT (10mA) scan and a BH-CT (10mA) scan (at end-expiration) of a 15cm segment of the body (the field of view of the PET scanner) will be performed with the tumor at the field center. These images will be used for both attenuation correction and registration of the serial image set, for the free-breathing and BH PET dynamic data sets respectively.

To further facilitate patient image registration, external fiducial markers may be placed on the patient's thorax.

A second set of three dynamic F-FMISO scans will be performed following the same sequence as outlined above for the baseline dynamic F-FMISO study, at 2 to 3 weeks (+/- 4 days) post-initiation of therapy.

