## **9.3 Pharmacokinetic Modeling of F-FMISO PET:**

The dynamic data of the F-FMISO radiotracer in the tumor must be supplemented by clearance data from the blood. Blood samples may be taken at pre-designated times during the F-FMISO PET scan. If the PET images contain the heart within the field of view, one IV blood sample (about 1-2 ml) will be drawn at 30-40 minutes post F-FMISO injection. If the heart is not within the PET FOV, a maximum of 9 IV blood samples (about 1-2 ml each) may be obtained at approximately the following time points: 1, 2, 3, 4, 5, 15, 30, 90 and 180 minutes post injection. A separate IV line (other than the one used for FMISO injection) will be used to draw the blood. These samples will be weighed and counted for the purpose of determining the blood clearance kinetics and the tumor input function.

Compartmental kinetic analysis of the dynamic  $^{18}\text{F}$ -FMISO PET images will be conducted using the blood clearance time activity curve as input function to the  $^{18}\text{F}$ -FMISO compartmental model. The kinetic rate constants  $k_1$ ,  $k_2$ , and  $k_3$  (trapping rate) will be deduced. As a first approximation, hypoxic sub-regions within the tumor will be defined based on a  $k_3 > 0.1$ . We will then re-assess this  $k_3$  threshold based on results from the first 12 patients.

The same kinetic analysis will be repeated for the 2nd baseline  $^{18}\text{F}$ -FMISO study. The kinetic rate constants from the first and second  $^{18}\text{F}$ -FMISO studies will be compared, as well as the geographic positions of the hypoxic sub-volumes within the tumor between the first and second scans.

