## 10.0 EVALUATION DURING TREATMENT/INTERVENTION

There will be no specific monitoring after the studies. All patients will be evaluated according to the standard of care for their lung cancer. Their imaging studies performed as part of standard of care every 3-4 months and their vital status will be periodically monitored for 3 years following treatment for the progression free survival and overall survival analyses.

	Day 0  BH F-FDG  PET/CT	F-FMISO1  (within 14 +/- 5 days after the baseline  F-FDG scan, and before starting therapy)	Mid Treatment Scans		Follow up
			F-FMISO2  Within occur two weeks +/- 4 days post initiation of therapy	F-FDG  (FDG: 3 to 4 weeks +/- 4 days post-initiation of therapy)	
Informed consent	X				
Review of your history and medication	X				
Physical exam	X				
Vital signs	X	X			
Standard clinical  F-FDG PET/CT scan	X		X		
 F-FMISO tracer injection		X 	X 	X	
Research PET scans	X	X	X	X	
Research blood draws		X	X		
Review of medical record for PFS and OS					X
Standard clinical CT of the chest					X 
Vital signs and Toxicity assessment 		X	X		

Table 1. Group 1: FMISO 2 Mid-Treatment Group Study Outline

	Day 0  F-FDG PET/CT	F-FMISO1  (within 14 +/- 5 days after the baseline  F-FDG scan, and before starting therapy)	Simultaneous F-FDG/F-FMISO 2  (at least one day after the first  F-FMISO scan but before starting therapy. This must also be within 14 +/- 5 days after baseline FDG scan)	Optional Mid Treatment F-FDG  (3 weeks +/- 4 days after RT)	Follow up
Informed consent	X				
Review of your history and medication	X				
Physical exam	X				
Vital signs	X	X			
Standard clinical  F-FDG PET/CT scan	X		X		
 F-FMISO tracer injection		X 	X 	X	
Research PET scans	X	X	X	X	
Research blood draws		X	X	X	
Review of medical record for PFS and OS					X
Standard clinical CT of the chest					X 
Vital signs and Toxicity assessment 		X			

Table 2. Group 2: Simultaneous FDG and FMISO group study outline

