## 11.2 F-FMISO PET Scan

### 11.2.1 F-FMISO PET Schedule

F-FMISO is a radiotracer which MSKCC holds an approved IND. In patients who agree to participate in this protocol, two F-FMISO PET Scans will be obtained within 5 days, at least 1 day after the baseline F-FDG-PET that is required as part of pretreatment enrollment criteria.

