## **12.0 CRITERIA FOR THERAPEUTIC RESPONSE/OUTCOME ASSESSMENT**

There are two primary goals for this study; first, to assess the reproducibility of kinetic analysis of dynamic  $^{18}\text{F}$ -FMISO PET images, in both BH and FB data sets, and second, to assess the prognostic value of hypoxia, as measured with  $^{18}\text{F}$ -FMISO PET, with OS and PFS in NSCLC. As explained above, the presence and extent of tumor hypoxia will be measured by means of kinetic analysis of dynamic  $^{18}\text{F}$ -FMISO PET images. Kinetic analysis parameters may be susceptible to breathing-induced motion artifacts due to patient respiration. Hence, the correlation of outcome to both the presence and extent of tumor hypoxia may be inaccurate. We will therefore conduct analyses based on BH- and FB- PET datasets, and then compare the results in order to assess the effect breathing on these parameters. This exploratory objective of tumor hypoxia correlation to clinical endpoints is dependent on time to tumor progression and death. We will follow up with these patients up to a maximum of three years. The table below summarizes the milestones of this research project.

Likewise, the predictive value of FDG PET may also be suspect due to breathing motion artifacts. In light of the discussion above, therefore, the secondary aim is to compare the predictive value of FDG PET when the data are acquired in BH versus in FB PET.

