## **14.0 BIOSTATISTICS**

This study will enroll 25 patients with non-small cell lung cancer (NSCLC) who will undergo treatment with definitive conventionally fractionated radiation therapy (RT), neoadjuvant chemotherapy, or chemo-RT. In addition to standard of care PET/CT scans, they will also be scanned twice at baseline (pre-treatment) with experimental  $^{18}\text{F}$ -FMISO scans.

Since some patients will have multiple lesions some of the statistical analyses will be lesion-based and some will be patient-based. This is explained in detail within each analysis but primarily, reproducibility analyses will be lesion-based and analysis of predictive values will be patient-based. Presence and extent of hypoxia will be analyzed twice, one lesion-based and the other patient-based. One of the primary objectives is to evaluate the reproducibility of kinetic analysis in serial, BH and Free-Breathing (FB), dynamic  $^{18}\text{F}$ -FMISO PET images. Hypoxia is measured by  $k_3$ , the trapping rate (see section 7.3). This will be analyzed both as a binary and a continuous variable: if any of the voxels

inside the tumor has a  $k3 > 0.1$  the tumor is defined to be hypoxic while its extent will be defined by the fraction of hypoxic volume which is the fraction of tumor volume with  $k3 > 0.1$ . Reproducibility will be evaluated using Cohen's kappa for presence of hypoxia and concordance correlation coefficient for the extent of hypoxia. This will be a lesion-based analysis and multiple observations per patient will be taken into account using a variance inflation factor estimated from the intraclass correlation coefficient.

Another primary objective is to compare the presence and extent of hypoxia with the clinical outcome (see section 7.3 and above for the definition of hypoxia). Previous studies showed comparable outcomes for stage IIIA (which is the majority treated) when following either of the two treatment arms considered in this study (51, 52).

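### Section 14.0 bases a primary FMISO reproducibility analysis on two pre-treatment scans, but the schema, 9.2 and Table 1 put the second stand-alone scan after therapy starts, so no test-retest pairs are identified

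*Combined protocol and SAP*

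**What the plan says.** **Text that puts both scans before treatment.** Section 14.0 enrols 25 patients and states that "they will also be scanned twice at baseline (pre-treatment) with experimental" FMISO scans. It calls reproducibility one of the primary objectives and plans a lesion-based analysis with Cohen's kappa "for presence of hypoxia and concordance correlation coefficient for the extent of hypoxia". Section 9.3 repeats the kinetic analysis for a second baseline FMISO study and compares the rate constants, "as well as the geographic positions of the hypoxic sub-volumes within the tumor between the first and second scans". Section 11.2.1 says two FMISO "PET Scans will be obtained within 5 days, at least 1 day after the baseline" FDG scan. Sections 3.3 (opening paragraph) and 4.1 also set reproducibility in the period before treatment. Section 12.0 ranks it first: "There are two primary goals for this study; first, to assess the reproducibility of kinetic analysis of dynamic" FMISO images. Section 12.0 gives no scan timing.

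**Text that puts the second scan on treatment.** For the second FMISO scan in Group 1, the Schema in Section 1.0 says: "This scan will occur two weeks +/- 4 days after the start of radiotherapy or the radiation portion of combined chemo-radiation". Section 9.2 places the second set of dynamic scans "at 2 to 3 weeks (+/- 4 days) post-initiation of therapy". The Table 1 column for the second FMISO scan reads "Within occur two weeks +/- 4 days post initiation of therapy". Section 3.3 also describes a scan about two weeks into therapy, and Section 11.2.5 refers to the two FMISO scans as baseline and follow-up.

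**Objectives.** Section 2.0 does not list reproducibility among its primary or secondary objectives, and it mentions a mid-treatment FMISO scan that is optional for the dual-tracer patients.

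**The concern.** Kappa and the concordance correlation coefficient measure reproducibility only if the two scans observe the same biological state. Section 14.0 secures this by requiring both before treatment. If the second stand-alone scan is acquired after radiation has started, an analyst following 14.0 has no pairs of the kind it describes, and a stated primary analysis cannot be carried out.

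The list of primary objectives is also unsettled: 12.0 and 14.0 include reproducibility and 2.0 does not. The power sentence in 14.0 has a related looseness. It contrasts groups with low and high change, while the next sentence dichotomises extent of hypoxia and the Cox model uses extent as its covariate.

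**Working it through.** The plan states no sample size, precision or power for kappa or concordance, so there is no such figure to reproduce. The check is a count of scans and of usable pairs.

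**1. Stand-alone FMISO scans provided for per patient.**
- Section 11.2.3: CT dose per FMISO study is 3 × 0.066 + 3 × 0.771 = 2.511, stated as 2.51 rad. Two studies give 2 × 2.51 = 5.02 rad, the plan's own figure. Two baseline scans plus one mid-treatment scan would give 3 × 2.51 = 7.53 rad.
- Section 11.2.2: injections on each of two FMISO scan days.
- Section 11.2.5, Table 6: one column for two 10 mCi FMISO studies, described in the text as baseline and follow-up.
- Section 7.0: $100 per completed FMISO session, up to $200, so 2 sessions. This is supporting evidence only. Group 2 patients could have three FMISO-containing sessions (first scan, dual-tracer scan, optional mid-treatment scan) under the same cap.

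Result: two stand-alone scans. A patient who has one at baseline and one mid-treatment has none left for a second baseline scan.

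**2. Like-for-like pre-treatment pairs.**

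| Source | Pairs |
|---|---|
| 14.0 (with 9.3 and 11.2.1) | 25 |
| 1.0, 9.2 and Tables 1 and 2 | 0 identified |
| Group 2 first scan and dual-tracer scan | 5, not like for like |

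The Group 2 dual scan (9.4) uses 8 mCi FMISO, with 8 mCi FDG injected about 45 minutes later during a continuous acquisition. The stand-alone scan (9.2) uses 10 mCi FMISO alone in three segments. Section 1.0 gives the dual scan's purpose as testing how accurately the FMISO signal can be extracted.

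**3. Patients outside the mid-treatment scan.** Section 1.0 gives that scan to 25 patients on RT or concurrent chemo-RT, which uses up the 25 in 14.0. Section 4.1 instead describes 10 RT or chemo-RT patients and 16 neoadjuvant patients (10 + 16 = 26, against its stated total of 25). On 4.1's counts up to 16 patients would have no mid-treatment FMISO scan under 1.0, and two baseline scans would fit their allowance. No passage assigns them two. Section 9.2 is not limited to RT patients and times the second set after therapy starts.

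**4. Precision if only Group 2 were used.** Fisher-z approximation, one lesion per patient assumed, tanh(atanh(r) ± 1.96/√(n − 3)). For an observed concordance of 0.8: n = 5 gives −0.28 to 0.99; n = 25 gives 0.59 to 0.91. Five pairs support description only.

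**5. Why a pre-treatment/mid-treatment pair is not a repeat (illustration).** Assume an error-free method, baseline prevalence p, a proportion r of hypoxic tumours resolving, and no new hypoxia. With q = p(1 − r), observed agreement is 1 − rp, chance agreement is pq + (1 − p)(1 − q), and kappa = (observed − chance)/(1 − chance). For p = 0.5 and r = 0.9: q = 0.05, observed 0.55, chance 0.50, kappa = 0.05/0.50 = 0.10, although true reproducibility is perfect. Over p from 0.9 to 0.4, kappa is 0.02 to 0.12 at r = 0.9, 0.17 to 0.55 at r = 0.5, and 0.44 to 0.83 at r = 0.2. The 90% is the head and neck figure cited in 3.3. Its transfer to NSCLC, and all the other values, are assumptions.

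**The case against.** The strongest reply is that nothing says the schema overrides 14.0. Sections 3.3, 4.1, 9.3, 11.2.1 and 14.0 all point to reproducibility before treatment. That stands: the defect is an unresolved contradiction, and the count of zero applies only to the schema as now written.

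A reader might infer that the two schedules can never coexist in this trial. The documents do not support that. The two-scan allowance is per patient, so the exclusion is shown only for patients who have the mid-treatment scan. Nor do they show that no pairs exist at all. Section 1.0 speaks of groups that are currently active, which leaves room for an earlier group; the documents neither confirm nor exclude one.

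A reader might also infer that the plan will compute kappa on baseline against mid-treatment scans. No passage says so, and 14.0 describes its pairs as pre-treatment. The illustration above shows why the exclusion deserves a sentence; it does not measure a planned error.

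Reproducibility might be read as breath-hold against free-breathing. That does not work: 12.0 wants it in both data sets, 9.3 compares a first and a second study, and both FMISO sets come from the same acquisition.

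Finally, the study is exploratory and its scans do not guide care. This limits the harm but does not make the analysis executable.

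**Conclusion.** Wrong as written. A primary analysis in 14.0 requires 25 pre-treatment FMISO pairs, and the current schema identifies none that are like for like. This rests on reading the dosimetry and scan-day provisions as two stand-alone scans per patient, and on treating the dual-tracer scan as a different measurement. Both readings follow from the protocol's own descriptions. It remains open whether neoadjuvant-only patients or an earlier group supply true pairs.

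What is at stake is the reproducibility result and the clarity of the primary objectives. The analysis of baseline hypoxia against PFS and OS needs only the first scan and is unaffected.

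**What to change.** 1. Reconcile the timing of the second FMISO scan and the list of primary objectives across Sections 1.0, 2.0, 3.3, 4.1, 9.2, 9.3, 10.0, 11.2.1, 12.0 and 14.0. This includes the different windows in 1.0 and Table 1 (two weeks) and 9.2 (two to three weeks). Which schedule is right is for the investigators to settle.
2. Add to 14.0: *Kappa and the concordance correlation coefficient are restricted to patients with two stand-alone pre-treatment FMISO scans, including any already collected, and the number of such patients will be reported. A pre-treatment and a mid-treatment scan are not repeat measurements and will not be analysed as reproducibility.*
3. If there are no such patients, remove reproducibility as a primary analysis and report the Group 2 comparison of sole and dual-tracer FMISO descriptively (n = 5).
4. Make the contrast in the power sentence match the covariate used, extent of hypoxia.

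Cost: text changes only, with no new scans or patients. The reproducibility claim may be lost or reduced to description.

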### 3.2 Hypoxia

Hypoxia is a characteristic feature of malignant tumors that has been well established (16-22). Unlike healthy tissues, tumors often grow at a rate that outgrows their blood supply resulting in the emergence of regions of hypoxia. Immunohistochemical studies have shown nests of hypoxic cells of up to several hundred micrometers in diameter, located at poorly perfused locations within the tumor (23-25). Hypoxia can create selective pressures that render the tumor more aggressive and radioresistant, and has been shown to exhibit an increased likelihood of locoregional recurrence, propensity for metastasis, and poor overall outcome. With invasive measurements, a hypoxia fraction HF2.5 (percentage of measurements <2.5 mmHg) was shown to be the most predictive factor for survival in head & neck cancer (HNC), with a threshold HF2.5 of 20% [17]. In NSCLC, 62% of patients exhibited a HF2.5 < 20% (26).

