The optimal method to quantitate hypoxia using F-FMISO is to perform compartmental analysis of the dynPET images (39-41). This is a method which uses kinetic information from dynamic scans to assess the rate of uptake and entrapment within the hypoxic tumor tissue. However, compartmental analysis is not meaningful on standard clinical PET images of the lung because of respiratory motion during the PET acquisition. Our group at MSKCC has developed a technique for Breath-Hold (BH) PET/CT imaging. During BH PET/CT, patients are asked to hold the breath for as long as possible, and data are acquired only during the time of the BH, using an in-house respiratory tracking device to monitor patient breathing motion (42). PET emission data will be acquired only while the patient is holding the breath as monitored by an external camera and chest sensor. This process will be repeated until a total of 3 min of BH PET data (equivalent to clinical setup) are acquired. We now propose a novel technique to acquire motion-free F-FMISO dynPET images of lung (one 15 cm field of view) to make accurate compartment analysis, and thus quantification of tissue hypoxia, possible. We shall acquire clinical F-FMISO dynPET images in Free-Breathing (FB) with the list mode (LM) option. During the dynamic PET study, the patient's breathing signal will be recorded simultaneously using an in-house developed tracking software assisted by a video camera. The camera is used to monitor the motion of fiducial markers positioned on the patient's abdomen. The patient's breathing signal will be correlated to the PET data on an event-by-event basis and then only those corresponding to end-expiration will be selected for the final PET images, thus resulting in motion-free images. Incorporating all the PET events from the same dynamic PET study results in the FB dynamic PET data set.

In PET/CT, CT images are used to correct for attenuation in the PET images. Spatial matching between PET and CT images is therefore crucial. Therefore, CT images at breathing phases matching those of the PET images will be acquired. PET data will be corrected for attenuation using the phase-matched CT images.

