Therefore, data from both groups of patients will be analyzed together. Historical data suggests 38% of patients will be free of recurrence at 3 years (53), which provides us with approximately 80% power to detect a hazard ratio of 3.0 between groups of low and high change. This calculation is based on a log-rank test and assumes that extent of hypoxia is dichotomized at observed median resulting in equal group sizes and maximal power. This is for planning purposes only. We will use Cox regression with extent of hypoxia as the covariate in two different ways: (1) lesion-based analysis with an estimating equations to account for multiple observations per patient; (2) patient-based where an aggregate measure of extent of hypoxia (sum of the fraction of tumor volumes with  $k3 > 0.1$  across all lesions) over all lesions within a patient) will be used as a covariate. In addition, a lesion and patient-based analyses for presence of hypoxia will also be considered where, for the patient-based analysis, the aggregate measure will be defined as presence of hypoxia in at least one of the lesions.

In an exploratory analysis to address the secondary objective of assessing the predictive value of FDG PET/CT in a group of twenty five lung cancer patients undergoing radiotherapy or concurrent chemoradiotherapy, we will use the concordance probability estimate from a proportional hazards regression model with SUV as the predictor for the outcomes of survival and progression-free survival. Time of origin will be the start time of therapy (neoadjuvant therapy, if applicable, concurrent chemoradiation or radiation alone otherwise). We will use these estimates to preliminarily determine whether BH PET/CT provides greater predictive capability than Free-Breathing (FB) PET/CT. Since these analyses are exploratory findings will be interpreted as hypothesis-generating.

We expect to accrue one patient a month for each of the two cohorts.

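### The any-voxel rule confounds presence of hypoxia with tumour size, lesion count and image noise, and makes it non-comparable between BH and FB FMISO images

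*Combined protocol and SAP*

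**What the plan says.** Section 14.0 derives two variables from the voxel-level trapping rate k3. For presence, the rule is: "This will be analyzed both as a binary and a continuous variable: if any of the voxels" in the tumour has k3 above 0.1, the tumour is hypoxic. Extent is the share of tumour volume above the same cut: "the tumor is defined to be hypoxic while its extent will be defined by the fraction of hypoxic volume". At patient level, for presence, "the aggregate measure will be defined as presence of hypoxia in at least one of the lesions". The patient-level extent is the sum of the hypoxic fractions over lesions.

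Presence has two uses. One is reproducibility: "Reproducibility will be evaluated using Cohen's kappa for presence of hypoxia and concordance correlation coefficient for the extent of hypoxia". The other is outcome, in lesion-based and patient-based analyses listed after those on extent.

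Section 9.3 treats 0.1 as provisional, with a re-assessment of the "threshold based on results from the first 12 patients". Section 3.3 explains how the FMISO BH set is made: of the events in the free-breathing list-mode scan, "only those corresponding to end-expiration will be selected for the final PET images, thus resulting in motion-free images". The FB set uses all events of that same scan. Section 12.0 plans the analyses in both sets and a comparison of the results. Section 6.1 requires a tumour of at least 2 cm and sets no upper limit.

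**The concern.** Presence is a maximum compared with a fixed cut: the highest voxel in a lesion, then the highest lesion in a patient. With any noise in k3, a larger tumour or an extra lesion gives more chances to pass 0.1 with no hypoxia at all. Tumour volume is plausibly prognostic in its own right, so an association of presence with PFS or OS could partly reflect size.

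The BH-FB comparison has a further problem. Both sets come from one scan and BH uses fewer events, so one tumour can be negative on FB and positive on BH through count noise alone. A difference in presence then cannot be put down to breathing motion.

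If most tumours become positive, kappa and the Cox contrast for presence both lose information. Moving the 0.1 cut after 12 patients would change how often this happens but would leave the any-voxel rule in place.

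**Working it through.** **The plan's own figures.** The documents give no figure for presence. The only one nearby is about 80% power at a hazard ratio of 3.0, for extent split at the median. With 25 × 0.62 = 15.5 events and a two-sided 5% test (no alpha is stated), Φ(√(15.5 × 0.25) × ln 3 − 1.96) = Φ(0.20) = 58%. That shortfall is a separate matter; 58% serves below only as a baseline.

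**Inputs.** From the documents: any-voxel rule, cut at 0.1, any-lesion rule, BH events a subset of FB events. Assumed, because the documents give none of them: spherical tumour; 0.05 mL voxels, of which one-eighth are effectively independent; Gaussian noise; a cut lying c noise SDs above the true k3 on FB; a share f of events kept on BH, so that the noise SD is multiplied by 1/√f; no motion effect.

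**Formulas.** Number of independent elements: n = (π/6)d³ / 0.05 / 8. Per-element false rate: q(FB) = P(Z > c) and q(BH) = P(Z > c√f). False presence: P = 1 − (1 − q)ⁿ.

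**Size.** With c = 3.09, q(FB) = 0.1%. At 2, 4 and 6 cm there are 84, 670 and 2,262 voxels, so n is about 10, 84 and 283, and P = 1%, 8% and 25%. If every voxel were independent, P would be 8%, 49% and 90%. With c = 5, q = 2.9 × 10⁻⁷ and even the 6 cm tumour (n = 283) gives only 0.008%.

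**Lesion count.** A 3 cm tumour is 14.1 mL, or 283 voxels, so n = 35. At c = 3.09, one such lesion gives 1 − 0.999³⁵ = 3%, and three give 1 − 0.999¹⁰⁵ = 10%.

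**BH v FB, same non-hypoxic 3 cm tumour (n = 35).**

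| Cut above true k3 (FB noise SDs) | Events kept on BH | q(BH) | False presence, FB | False presence, BH |
|---|---|---|---|---|
| 3.09 | one-third | 3.7% | 3% | 73% |
| 3.09 | half | 1.4% | 3% | 40% |
| 4 | half | 0.23% | 0.1% | 8% |
| 5 | one-third | 0.19% | about 0% | 7% |
| 5 | half | 0.02% | about 0% | 0.7% |

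**Extent under the same noise.** The expected false hypoxic fraction of a lesion is q, whatever n is. In the first row it is 0.1% on FB and 3.7% on BH; in the last, about 0% and 0.02%. Noise still shifts extent, and the patient-level sum adds q per lesion, but extent does not climb with tumour volume.

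**If most tumours become positive.** With 90% positive, power at a hazard ratio of 3.0 is Φ(√(15.5 × 0.09) × ln 3 − 1.96) = Φ(−0.66) = 25%, against 58% at an even split. For kappa = 0.6 (assumed) and 25 lesions, SE = √[po(1 − po) / (25(1 − pe)²)]. An even split has pe = 0.50 and po = 0.80, giving 0.16; 90% positive has pe = 0.82 and po = 0.928, giving 0.29.

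**Would a minimum fraction alone be enough?** Take 5% for illustration, which is at least 2 of 35 elements. In the first row, false presence becomes 0.06% on FB and 38% on BH. The minimum lowers false positives but does not equalise the two sets. Matching the counts would equalise them (both have the BH rate of q under this model) but would not by itself lower the false positives. The two steps do different jobs.

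**The case against.** Four points on the other side deserve weight.

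- **The effect may be trivial.** Voxel size, k3 noise, smoothing and the share of events kept are not given. A reader might infer that presence *is* merely a measure of size and noise. The documents do not support that: at low noise, false presence stays below 1% in both sets. This stands, and it limits the point to confounding of unknown size.
- **More BH positives could be real.** Section 3.5 says breathing blurs the target and lowers apparent uptake, so removing motion may properly reveal high k3. A reader might infer that a BH-FB difference is pure noise, or that BH is favoured. Neither follows. Noise raises BH positives, but it may also lower BH kappa and weaken the BH link with outcome, so the direction of bias in the predictive comparison is not fixed. This stands. It also shows why noise and motion need to be separated.
- **Extent already leads.** It is the basis of the power statement and the first Cox covariate, and it has its own reproducibility statistic. The study is exploratory and does not alter care. This stands and lowers the priority. Presence nevertheless remains part of a stated primary objective in Section 14.0.
- **The background does not contradict the rule.** Section 3.2 cites a fraction of readings, "with a threshold HF2.5 of 20"%, but for invasive measurements in head and neck cancer, and the plan's counterpart to it is extent. This stands: the citation shows that a fraction rule is natural, not that the any-voxel rule is an inconsistency.

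The improved signal-to-noise ratio in Section 3.6 is no answer. It concerns deep-inspiration breath-hold, where acquisition continues until three minutes of held data are collected, not the retrospectively gated FMISO series.

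**Conclusion.** The point holds in a limited form. As defined, presence is confounded with tumour size, lesion count and image noise, and presence on BH is not comparable with presence on FB, because BH is a lower-count subset of the same events. No safeguard appears in the plan.

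The direction of the effect on false presence follows from the rule itself; its size does not. For a non-hypoxic 3 cm tumour it runs from about 0% v 0.7% (cut 5 SD above true k3, half the events kept) to 3% v 73% (3.09 SD, one-third kept). Both ends rest on the assumed voxel size, voxel correlation, Gaussian noise and event retention. An observed BH-FB difference in presence would mix extra noise with real removal of motion blur. Extent is much less exposed. This is a cheap improvement, not a flaw that undermines the main outcome analysis.

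**What to change.** In Section 14.0, before analysis and blind to outcome:

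1. Replace the any-voxel rule with a minimum hypoxic fraction or minimum contiguous hypoxic volume. It should lie above a noise floor estimated from k3 in non-tumour tissue in the same field and the same image set. Settle it together with the threshold re-assessment in Section 9.3.
2. For the BH-FB comparison of presence, also reconstruct FB from the list-mode data down-sampled to the BH counts. BH against down-sampled FB then shows the effect of motion; full against down-sampled FB shows the effect of noise.
3. Add a sensitivity analysis of presence adjusted for tumour volume.

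Any numeric cut, such as 5% or 1 mL, is illustrative only, and the two are not interchangeable: 1 mL is 24% of a 2 cm tumour (4.2 mL) but 0.9% of a 6 cm tumour (113 mL).

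The cost is one revised definition, re-thresholding of images and some extra reconstruction, with no new scans. The downside is that very small hypoxic foci are no longer counted.
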